#### 4.3 End Points

##### 4.3.1 Primary Endpoint for Each Access Arm of the Study:

The study will have a primary safety endpoint for each arm of the study which is the rate of major vascular complications through 30 days, as defined by the Valve Academic Research Consortiumii (VARC-2).

##### 4.3.2 Secondary Endpoints:

The following secondary endpoints will be evaluated for each arm of the study.

1. The event rates at 30 days of the following:

- All-cause mortality
- Cardiovascular mortality
- Disabling stroke
- Non-disabling stroke
- Life-threatening bleeding requiring transfusion
- Acute kidney injury requiring dialysis
- Composite of
  - periprocedural encephalopathy

**Clinical Investigational Plan**

- all stroke
  - all TIA
2. The event rates at 1 year of the following:
- All-cause mortality
  - Cardiovascular mortality
  - Disabling stroke
  - Moderate and severe aortic regurgitation
3. Improvement from baseline as compared to 30 days by:
- NYHA functional classification
  - Six minute walk test
  - Effective orifice area
4. Acute device success defined as:
- Absence of procedural mortality
  - Correct positioning of a single prosthetic heart valve into the proper anatomical location
  - Intended performance of the prosthetic heart valve
    - mean aortic valve gradient <20 mmHg
    - peak velocity < 3 m/s
    - no moderate or severe prosthetic regurgitation

In addition successful access, delivery and deployment of the valve and retrieval of the delivery system will be collected.

**4.4 Study Population**

The subjects targeted for this study have symptomatic severe native aortic stenosis and are deemed high operable risk in the medical opinion of the center's heart team and subsequently the Subject Selection Committee (see section 7.2 for details). In the opinion of the implant team, the preferred access route for the patients enrolled in the trial should be alternate access (subclavian/axillary or direct aortic). The determination of the preferred route may take into account patient specific anatomical considerations and other risk factors as well as implanter and patient preference. To participate in this study, patients must meet all inclusion and none of the exclusion criteria for the study.

**4.4.1 Inclusion Criteria**

To participate in this clinical study, the subject must meet all of the following inclusion criteria:

1. Subject has provided written informed consent prior to uploading CT scan to core lab.
2. Subject is  $\geq 18$  years of age or legal age in host country.
3. Subject's aortic annulus diameter meets the range indicated in the Instructions for Use as measured by multislice CT conducted within 180 days prior to the index procedure.
4. Subject has senile degenerative aortic stenosis seen by echocardiography within 90 days of index procedure as measured by one of the following:
  - a. Mean gradient  $\geq 40$  mmHg
  - b. Peak velocity  $\geq 4.0$  m/s
  - c. Doppler Velocity Index < 0.25
  - d. Aortic valve area (AVA) of < 1.0 cm^2 or indexed EOA < 0.6 cm^2/m^2

**Clinical Investigational Plan**

5. Subject has symptomatic aortic stenosis as demonstrated by NYHA Functional Classification of Class II or greater or other symptoms of aortic stenosis (e.g. syncope)
6. Subject is deemed high operable risk and preferred TAVI delivery route is alternative access (subclavian/axillary or direct aortic) per the medical opinion of the center's heart team and confirmed by SSC
  - a. High risk is defined as STS mortality  $\geq 8\%$  or documented heart team agreement  $\geq$  high risk for SAVR due to frailty or co-morbidities

**4.4.2 Exclusion Criteria**

Subjects are not eligible for clinical study participation if they meet any of the following exclusion criteria:

1. Subject is unwilling or unable to comply with all study-required follow-up evaluations.
2. Subject has a documented history of a cerebral vascular accident (CVA) or transient ischemic attack (TIA) within 6 months (less than or equal to 180 days) prior to the index procedure.
3. Subject has carotid artery disease requiring intervention.
4. Subject has evidence of a myocardial infarction (MI) within 30 days prior to patient index procedure.
5. Subject has a native aortic valve that is congenitally unicuspid, bicuspid, quadricuspid or non-calcified as seen by echocardiography.
6. Subject has severe mitral valvular regurgitation.
7. Subject has severe mitral stenosis.
8. Subject has a pre-existing prosthetic cardiac device, valve, or prosthetic ring in any position.
9. Subject refuses any blood product transfusion.
10. Subject has resting left ventricular ejection fraction (LVEF) less than 20%.
11. Subject has documented, untreated symptomatic coronary artery disease (CAD) requiring revascularization.
12. Subject has had a percutaneous interventional or other invasive cardiovascular or peripheral vascular procedure less than or equal to 14 days prior to index procedure.
13. Subject has severe basal septal hypertrophy that would interfere with transcatheter aortic valve placement.
14. Subject has a history of, or is currently diagnosed with endocarditis.
15. There is imaging evidence of intracardiac mass, thrombus, or vegetation.
16. Subject is considered hemodynamically unstable (requiring inotropic support or mechanical heart assistance).
17. Subject is in acute pulmonary edema or requiring intravenous diuretic therapy to stabilize heart failure.
18. Subject with severe pulmonary disease as determined by STS score.
19. Subject is on chronic oral steroid therapy.
20. Subject has a documented hypersensitivity or contraindication to anticoagulant or antiplatelet medication.
21. Subject has renal insufficiency as evidenced by a serum creatinine greater than 3.0 mg/dL (265.5  $\mu$ mol/L) or end-stage renal disease requiring chronic dialysis.
22. Subject has morbid obesity defined as a BMI greater than or equal to 40.
23. Subject has ongoing infection or sepsis.
24. Subject has uncontrolled blood dyscrasias as defined: leukopenia (WBC < 3000  $\text{mm}^3$ , acute anemia (Hb < 9g/dL), thrombocytopenia (platelet count < 50,000 cells/ $\text{mm}^3$ ).

**Clinical Investigational Plan**

25. Anatomy falling outside the recommended values in the IFU, unless specifically approved by the Subject Selection Committee.
26. Subject has an active peptic ulcer or has had gastrointestinal (GI) bleeding within 90 days prior to the index procedure.
27. Subject is currently participating in another investigational drug or device study, unless approved by the Sponsor.
28. Subject has/had emergency surgery for any reason within 30 days of the index procedure.
29. Subject has a life expectancy less than 1 year.
30. Subject has other medical, social or psychological conditions that, in the opinion of the site Heart Team or the Subject Selection Committee, preclude the subject from study participation.
31. Subject is diagnosed with a state of dementia which would fundamentally complicate rehabilitation from the procedure or compliance with follow-up visits.
32. Subject has a documented allergy to contrast media that cannot adequately be treated, nitinol alloys, porcine tissue, or bovine tissue.
33. Significant aortic disease including abdominal aortic or thoracic aneurysm defined as maximal luminal diameter 5cm or greater
34. Subjects with severe pulmonary hypertension and severe RV dysfunction
35. Subjects with hypertrophic cardiomyopathy

**4.4.3 Transaortic Subject Cohort Specific Exclusion Criteria**

Subjects are not eligible for participation in the TAO access arm if they meet any of the following exclusion criteria:

1. Subject has a chest condition (anatomical or otherwise) that prevents TAO access.
2. Subject has pre-existing patent RIMA graft that would preclude access.
3. Subject has a porcelain aorta, defined as an extensive circumferential calcification of the ascending aorta that would complicate TAO access.

**4.4.4 Subclavian/Axillary Subject Cohort Specific Exclusion Criteria**

Subjects are not eligible for participation in the subclavian/axillary access arm if they meet any of the following exclusion criteria:

1. Subject's access vessel (subclavian/axillary) diameter will not allow for introduction of the 18/19 Fr delivery system.
2. Subject's subclavian/axillary arteries have severe calcification and/or tortuosity.
3. Subject has a history of LIMA/RIMA graft that would preclude access

**5.0 Procedures****5.1 Informed Consent Process**

Prior to enrolling in the clinical study and conducting study-specific procedures, all subjects will be consented, as required by applicable regulations and the center's EC. Informed consent must be obtained from each subject, signed and dated by the subject and by the person obtaining the consent.

The Principal Investigator or his/her authorized designee will conduct the Informed Consent Process. This process will include a verbal discussion with the subject on all aspects of the clinical study that are relevant to the subject's decision to participate in the clinical study. The subject will be given enough time to review the consent and ask any questions regarding the study.

## Clinical Investigational Plan

The subject shall be provided with the informed consent form that is written in a language that is understandable to the subject and has been approved by the center's EC. Failure to obtain informed consent from a subject prior to study enrollment should be reported to Abbott within 5 working days and to the reviewing center's EC consistent with the center's EC reporting requirements.

### 5.2 Subject Screening

Potential study subjects should be evaluated for study participation by site staff. This site staff evaluating the potential subject should be trained on the CIP and delegated to do so.

Subjects meeting the inclusion/exclusion criteria will be fully informed about the study and asked to participate. If the subject agrees, a duly signed and dated Patient Informed Consent will be obtained. Patients who do not meet the inclusion/exclusion criteria will not be eligible to participate in this study.

### 5.3 Point of Enrollment

Subjects are considered enrolled in the study from the moment the subject has provided written Patient Informed Consent.

### 5.4 Study Activities

Table 2. Study Activity Definitions

Study Activity Definitions	
Study Activity	Definition
Adverse Event Assessment	Adverse events will be documented according to definitions in Appendix D.
Barthel Index	A scale used to measure performance in activities of daily living (ADL). Each performance item is rated on this scale with a given number of points assigned to each level or ranking. It uses ten variables describing ADL and mobility where a higher number is associated with a greater likelihood of being able to live at home with a degree of independence following discharge from the hospital.
Blood Work	Blood lab tests will be collected at each required interval. The specific lab tests are indicted in Table 4
Cardiac Rhythm Monitoring	Assessment of heart rate, QRS and dominant rhythm preprocedure and during the procedure.
Chest X-Ray	Imaging conducted at Baseline per institutional guidelines.
Coronary and Aortic Angiogram with Runoff	Angiographic imaging off aortic arch the coronary, subclavian and axillary arteries. Assessment to be conducted per institutional guidelines.
CT Scan	Assessment to be conducted per institutional guidelines.
Echocardiography	Each site is responsible for performing the echocardiogram (echo) according to the Echocardiographic protocol. Echocardiogram will be copied to CD/DVD (or other large media storage device) and provided to an Echocardiographic Core Lab for evaluation.
Electrocardiogram (ECG)	Assessment of dominant rhythm, heart rate, and QRS interval via 12-lead.

**Clinical Investigational Plan**

Frailty Index	Used to assess if frailty is a high risk factor for subjects. Frailty index assessment is defined in APPENDIX G: FRALITY ASSESSMENT
Informed Consent	An Ethics Committee and Sponsor-approved Informed Consent must be obtained.
Medical History	General medical history of the patient: 

• Previous cardiovascular operations

• Coexisting cardiovascular diseases

• Clinically significant peripheral vascular disease

• Previous peripheral vascular operations

• Other coexisting medical conditions (eg, diabetes, hypertension, kidney and lung disease, endocarditis)

Medication Assessment	Only the following medication will be collected at each specified interval: 

• Beta Blockers

• Calcium Channel Blockers

• Anticoagulants

• Antiplatelet agents including Aspirin

• Diuretics

• ACE-Inhibitors

• Angiotensin Receptor Blocker (ARBs)

Modified Rankin Stroke Scale	
This assessment must be completed by a rater who has a current certificate that demonstrates completion of an accredited training program for this stroke scale, using the structured interview found in (APPENDIX H: SCALES).
 
The modified Rankin Scale (mRS) is functional measurement to assess the degree of disability or dependence in the daily activities of people who have suffered a stroke.

NIH Stroke Scale	
This assessment must be completed by a rater who has a current certificate that demonstrates completion of an accredited training program for this stroke scale.
 
The NIHSS is an 11-item neurologic examination stroke scale used to evaluate the effect of acute cerebral infarction on the levels of consciousness, language, neglect, visual-field loss, extraocular movement, motor strength, ataxia, dysarthria, and sensory loss. Certified personnel rate the patient's ability to answer questions and perform activities. Ratings for each item are scored with 3 to 5 grades with 0 as normal, and there is an allowance for untestable items.

NYHA Classification	The New York Heart Association (NYHA) Functional Classification provides a simple way of classifying the extent of heart failure and defined in APPENDIX I : NYHA CLASSIFICATION.
Physical Assessment	
At the baseline visit the following measurement must be assessed:
 

• Age on consent date

• Gender

• Height

 
The following measurements must be assessed at all visits:
 

• Weight

**Clinical Investigational Plan**

	

• Heart rate

• Heart rhythm

• Physical Assessment

Procedure Information	Procedure information must be collected including: 

• Pre-procedure Information

• Procedure Information

• Procedure Evaluation

• Post-procedure Information

Procedural imaging	All imaging collected during the procedure (intra-procedure) such as the cineangiogram and/or echocardiography should be collected and provided to the Sponsor.
QoL Questionnaire	EQ-5D 3L is a standardized instrument for use as a measure of health outcomes. The process to complete this questionnaire is indicated in APPENDIX F: QUALITY OF LIFE-EQ-5D 3L.
Surgical Risk Assessment	Surgical Risk Assessment tools Consists of the 3 assessments as defined in Appendix E: Risk Calculations: 

• Logistic EuroSCORE

• EuroSCORE II

• STS Risk Score

Six Minute Walk Test	Used to quantitatively assess submaximal exercise tolerance as defined in APPENDIX J: ATS GUIDELINES FOR THE SIX MINUTE WALK TEST.

**5.5 Procedures**

The clinical study will be conducted in accordance with the CIP. All parties participating in the conduct of the clinical study will be qualified by education, training, or experience to perform their tasks and this training will be documented appropriately. The data collection elements required for each follow-up are summarized in Table 3 below.

**Abbott**SJM-CIP-10144 Ver.D  
Study Name: Portico Alternative Access**Clinical Investigational Plan****Table 3: List of all study specific activities/procedures**

Follow-up procedure scheme							
Study Activity Visit window [days]	Baseline (within 30 days)	Procedure	Discharge [+0 to 7 days]	30-Day [-7/+14 days]	6-Month [±30 days]	1-Year [±30 days]	90 day visit after neuro event [±14 days]
Informed Consent	X						
Demographics	X						
Medical History	X						
Surgical Risk Assessment	X						
Coronary and Aortic Angiogram with runoff	X ‡						
Physical Assessment	X		X	X	X	X	
Barthel Index	X		X	X		X	X
Modified Rankin Stroke Scale (mRS)	X			X		X	X
NIH Stroke Scale (NIHSS)	X		X	X		X	X
Echocardiogram	X	X §	X	X	X	X	
CT Scan	X *						
Cine angiogram		X §					
Electrocardiogram (ECG)	X		X	X	X	X	
Chest x-ray	X						
Cardiac Rhythm Monitoring		X					
Blood Work	X	X ¶	X	X		X	
NYHA Classification	X			X	X	X	

**Abbott**

SJM-CIP-10144 Ver.D  
Study Name: Portico Alternative Access

## Clinical Investigational Plan

Study Activity Visit window [days]	Baseline (within 30 days)	Procedure	Discharge [+0 to 7 days]	30-Day [-7/+14 days]	6-Month [±30 days]	1-Year [±30 days]	90 day visit after neuro event [±14 days]
Frailty Index	X			X		X	
QoL Questionnaire	X			X		X	
Six Minute Walk Test	X			X		X	
Medication Assessment	X		X	X	X	X	
Adverse Events Assessment	X	X	X	X	X	X	

‡ Coronary and aortic angio may be completed up to 120 days prior to index procedure

\* CT scan may be completed up to 180 days prior to index procedure

§ All index procedure imaging must be sent to Abbott

▫ Index procedure bloodwork is tested twice (See Table 4):

**Clinical Investigational Plan****5.6 Enrollment Visit**

The baseline visit procedures must take place within 30 days of the index procedure. It is not necessary to repeat the coronary and aortic angiogram, if completed within 120 days of the planned index procedure. It is not necessary to repeat the CT scan (#12) if it will be completed within 180 days of the planned index procedure. The baseline visit consists of the following activities:

1. Obtain Informed Consent and Data Protection Form
2. Medical History including current diagnosis and Demographics
3. Initial Screening: Perform an initial screening to determine study eligibility
4. Chest X-Ray (CXR)
5. Surgical Risk Assessment
6. Coronary and Aortic Angiogram with runoff
7. Physical Assessment
8. Barthel Index
9. Modified Rankin Stroke Scale
10. NIH Stroke Scale
11. Echocardiogram
12. Computed Tomography (CT) Scan (required for sizing)
13. Electrocardiogram (ECG)
14. Blood work
15. New York Heart Association (NYHA) Functional Classification
16. Frailty Index Assessment
17. Quality of Life Questionnaire (QoL)
18. Six Minute Walk Test
19. Medication Assessment

**5.7 Implant/Procedure**

The medical team performing the study procedure will typically consist of:

- the primary cardiac surgeon at the site who will perform the TAO procedure
- the primary interventional cardiologist at the site who will perform the subclavian/axillary procedure
- second operator (cardiac surgeon or interventional cardiologist) who is recommended to be present during the procedure
- perfusionist
- anesthesiologist

At least one transcatheter aortic valve may be deployed via the physician determined alternative access pathway in every subject who has signed the Informed Consent Form, and Data Protection Form. Although not recommended, if a physician determines it is in the best interest of the subject to have a second transcatheter aortic valve placed, a subject may receive an additional transcatheter aortic valve.

The procedure visit will consist of the following activities:

**5.7.1 Pre procedure Activities**

1. Blood work (within 72 hours prior to index procedure, refer to Table 4)
  - Urea
  - Creatinine

**Clinical Investigational Plan**

## 2. ECG

**5.7.2 Procedure Activities**

1. Assess for adverse events
2. Document transcatheter aortic valve deployment information
3. Cardiac Rhythm Monitoring
  - Rhythm changes will be monitored and recorded at the following time points:
    - a. Immediately post valvuloplasty (if applicable)
    - b. After valve deployment and system retrieval
4. Procedural imaging (angiogram, intra-procedure echocardiography)

**5.7.3 Post Procedure Activities**

1. Blood work (within 48 hours post implant, refer to Table 4)
  - Creatinine
  - Urea

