**5.8 Scheduled Follow-ups****5.8.1 Discharge Visit**

The discharge visit will take place at the time of hospital discharge or 7 days post implant, whichever occurs first. Discharge testing maybe completed the day after procedure up until discharge or within 7 days if the subject has yet to be discharged. The discharge assessment will include:

1. Physical assessment
2. Barthel Index
3. NIH Stroke Scale
4. Echocardiography (to be performed between 24 hours and 7 days post implant)

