## Clinical Investigational Plan

**Table 4. Laboratory Scheme**

Lab Test	Baseline	Procedure		Discharge	30 days, & 1 Year
		Pre	Post		
Complete Blood Count 
 
White Blood Cell Count
 
Red Blood Cell Count
 
Hemoglobin
 
Hematocrit
 
	X			X	
Platelet count	X			X	
Urea and Creatinine	X	X*	X**	X	X
BNP or ProBNP	X			X	X
INR (if subject is on Coumadin/Warfarin)	X				
Troponin or CK, CK-MB	X				
Albumin	X				X

\* Within 72 hours before index procedure

\*\*Within 48 hours after index procedure

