### **Bleeding (VARC2)**

#### **Life-threatening or disabling bleeding**

- Fatal bleeding (BARC type 5) **OR**
- Bleeding in a critical organ, such as intracranial, intraspinal, intraocular, or pericardial necessitating pericardiocentesis, or intramuscular with compartment syndrome (BARC type 3b and 3c) **OR**
- Bleeding causing hypovolemic shock or severe hypotension requiring vasopressors or surgery (BARC type 3b) **OR**
- Overt source of bleeding with drop in hemoglobin of greater than or equal to 5 g/dL or whole blood or packed red blood cells (RBCs) transfusion greater than or equal to 4 U (BARC type 3b). *Given 1 U of packed RBC typically will raise blood hemoglobin concentration by 1 g/dL, an estimated decrease in hemoglobin will be calculated.*

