#### **Major bleeding (BARC type 3a)**

- Overt bleeding either associated with a drop in the hemoglobin level of at least 3.0 g/dL or requiring transfusion of 2 or 3 units of whole blood/RBC, or causing

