
Vascular Access Site and Access-Related Complications (VARC2)
	
Major vascular complications
 
 
Any aortic dissection, aortic rupture, annulus rupture, left ventricle perforation, or new apical aneurysm/pseudo-aneurysm or
 
Access site or access-related vascular injury (dissection, stenosis, perforation, rupture, arteriovenous fistula, pseudoaneurysm, hematoma, irreversible nerve injury, compartment syndrome, percutaneous closure device failure) leading to death, life-threatening or major bleeding*, visceral ischaemia or neurological impairment or
 
Distal embolization (non-cerebral) from a vascular source requiring surgery or resulting in amputation or irreversible end-organ damage or
 
The use of unplanned endovascular or surgical intervention associated with death, major bleeding, visceral ischaemia or neurological impairment or
 
Any new ipsilateral lower extremity ischemia documented by patient symptoms, physical exam, and/or decreased or absent blood flow on lower extremity angiogram or
 
Surgery for access site-related nerve injury or
 
Permanent access site-related nerve injury
 
 
Minor vascular complications
 
 
Access site or access-related vascular injury (dissection, stenosis, perforation, rupture, arteriovenous fistula, pseudoaneurysms, hematomas, percutaneous closure device failure) not leading to death, life-threatening or major bleeding*, visceral ischaemia or neurological impairment or
 

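### The required haemoglobin samples may not show the 3.0 g/dL fall that alone decides whether some access-site bleeds count towards the primary endpoint

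*Combined protocol and SAP*

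**What the plan says.** **Sampling.** Table 4 (section 5.10) marks "Complete Blood Count", the panel that contains haemoglobin, at baseline and discharge only. Its two procedure columns and its column for 30 days and 1 year are blank. The only row marked around the procedure is "Urea and Creatinine". Sections 5.7.1 and 5.7.3 agree: "Blood work (within 72 hours prior to index procedure, refer to Table 4" and "Blood work (within 48 hours post implant, refer to Table 4" each list only those two analytes. Section 5.6 lets baseline assessments fall up to 30 days before the procedure. For the later sample, section 5.8.1 says: "Discharge testing maybe completed the day after procedure up until discharge or within 7 days if the subject has yet to be discharged".

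**Classification.** In Appendix D an access-site or access-related injury is a major vascular complication if it leads to "death, life-threatening or major bleeding*, visceral ischaemia or neurological impairment", and a minor one if it does not. One way to reach major bleeding is "Overt bleeding either associated with a drop in the hemoglobin level of at least 3.0 g/dL". Life-threatening bleeding has its own haemoglobin criterion, a drop of at least 5 g/dL. Under that heading Appendix D credits about 1 g/dL per unit of red cells and says "an estimated decrease in hemoglobin will be calculated". It does not say which two samples define the drop.

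**Use.** Section 6.2.1 makes major vascular complications through 30 days the primary endpoint in each access arm. Section 6.2.1.1 reports it as a proportion with an exact 95% upper limit.

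**The concern.** For some access-site bleeds the primary endpoint depends on a laboratory change, and the plan does not schedule the samples that would measure it. The reference value may be a month old. The single later sample may precede the lowest value or follow recovery from it. A bleed between discharge and day 30 has no scheduled haemoglobin at all, although the endpoint runs to day 30.

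Blood is already drawn close to the procedure on both sides, but for kidney function only. The post-procedure draw matches the 48-hour window of the kidney-injury definition in Appendix D. The laboratory criterion inside the primary endpoint has no such matching sample.

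At stake is the count of a rare event in arms of 45. The same events feed the termination table in section 14.0 (6 of 20, 8 of 30, 9 of 40), so a missed event would also weaken that safeguard.

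**Working it through.** **1. Which bleeds are exposed.** Appendix D gives many routes to a major vascular complication that need no haemoglobin value, among them aortic dissection or rupture, annulus rupture, ventricular perforation, limb ischaemia and nerve injury. Within the bleeding route, these also suffice without one: transfusion of 2 or more units, surgery, hospitalization caused by the bleed, permanent injury, shock, and critical-organ or fatal bleeding. The exposed case is an overt access-site bleed with none of these. For it, the 3.0 g/dL fall decides between major and minor.

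The 5 g/dL fall does not. It separates life-threatening from major bleeding, and either grade already makes the complication major. It matters for the secondary endpoint of life-threatening bleeding.

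**2. What the required samples can show.** The values here are illustrative and are not from the documents. Take haemoglobin of 12.0 at baseline, 8.7 on day 1 and 10.0 at a day-6 discharge draw, with no transfusion.
- Actual fall: 12.0 − 8.7 = 3.3, so major.
- Fall from the required samples: 12.0 − 10.0 = 2.0, so minor.

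The error can also run the other way. Suppose 12.0 is an older baseline, 10.0 the value just before the procedure and 8.7 the discharge value.
- Fall from the required samples: 12.0 − 8.7 = 3.3, so major.
- Actual fall: 10.0 − 8.7 = 1.3, so minor.

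**3. The plan's own figure.** Section 6.3 uses a rate of 5.9% and 45 subjects. Expected events are 0.059 × 45 = 2.655. The exact (Clopper-Pearson) 90% interval with x = 2.655 and n = 45 is 1.45% to 15.32%, as the plan states. Its upper end is the one-sided 95% upper limit.

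**4. Effect of one reclassified subject.** The rate moves by 1/45 = 2.2 points. The upper limit is the 0.95 quantile of a Beta(x + 1, 45 − x) distribution:

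| Events | Rate | One-sided 95% upper limit |
|---|---|---|
| 2/45 | 4.4% | 13.34% |
| 3/45 | 6.7% | 16.34% |
| 4/45 | 8.9% | 19.20% |

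The steps are 16.34 − 13.34 = 3.00 and 19.20 − 16.34 = 2.86 points. With 2 or 3 events expected, one event is a third or a half of the total.

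**5. How often.** The documents give no frequency. As an assumption only, let a fraction m of true events be missed. The expected observed rate is p(1 − m), and the chance of at least one miss in an arm is 1 − (1 − pm)^45:

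| True rate p | m = 10% | m = 20% | m = 30% |
|---|---|---|---|
| 5.9%: observed rate | 5.3% | 4.7% | 4.1% |
| 5.9%: chance of a miss | 23% | 41% | 55% |
| 11.9%: observed rate | 10.7% | 9.5% | 8.3% |
| 11.9%: chance of a miss | 42% | 66% | 81% |

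This table covers missed events only. It does not cover false events from an out-of-date baseline.

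**The case against.** The strongest reply is that adjudication is not confined to scheduled samples. Appendix D does not tie the drop to Table 4. Section 9.2 makes every vascular complication reportable within 72 hours, requires records of the later medical course to be kept and submitted as applicable, and lets the sponsor ask for more information. Section 11.0 provides for full verification of available source documents. In the first illustration, a day-1 value of 8.7 that had been measured locally would be in the source record and could reach the Clinical Event Committee (CEC). The CEC charter (section 7.1) and the case report forms (Appendix L) are separate documents and may already ask for the lowest value.

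Much of this stands. It narrows the problem to bleeds where no clinical haemoglobin was taken near the lowest point, or where the value did not reach the CEC. It does not close the gap. The plan does not require such a value, the per-event data list in section 9.2 does not include it, and no reference sample is named.

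It is also true that a shift of 2.2 points per subject applies to any misclassification at this sample size, and that all three upper limits above lie below 23.3%, the top of the literature range in section 6.6. Going from 3 to 4 events takes the limit past 16.4%, the top of the pooled interval quoted there, but the plan sets no pass or fail rule on either figure.

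**Conclusion.** The point holds as a gap in ascertainment for a limited group: overt access-site bleeds that meet no other qualifying criterion. For them the required samples may not show a fall of at least 3.0 g/dL, or may measure it against an out-of-date value. Each reclassified subject moves an arm's rate by 2.2 points and the upper limit by about 3. The number of such subjects is unknown, and the miss fractions above are assumptions.

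A reader might infer three stronger things, and the documents support none of them:
- **That the primary endpoint as a whole rests on haemoglobin.** Most of its routes do not need a value.
- **That classification will differ between access arms or sites because of length of stay.** No length of stay is given by arm or site, and discharge testing may start the day after the procedure in any subject.
- **That the reported rate will be too low.** A late sample pushes it down, but an old baseline can push it either way.

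This is a cheap improvement worth making. It does not show that the planned analysis is invalid.

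**What to change.** 1. In Table 4 and sections 5.7.1 and 5.7.3, add haemoglobin to the two draws already scheduled, within 72 hours before and within 48 hours after the procedure.
2. The 48-hour draw may itself be taken before the lowest point, and bleeds may follow discharge. So, for every reported bleeding or vascular complication through 30 days, give the CEC the last pre-procedure haemoglobin, the lowest local post-procedure value with date and time, and the units transfused with date and time. If the charter or case report forms already provide this, say so in the plan.
3. Define the drop as the last pre-procedure value minus the lowest post-procedure value, adding 1 g/dL per unit only for units given between those two samples. Without that limit the rule overcounts. A fall from 12.0 to 9.5 is 2.5, but one unit given after the low value would turn it into 3.5 and cross the 3.0 threshold.
4. State whether the transfusion correction, which Appendix D gives under life-threatening bleeding, also applies to the 3.0 g/dL threshold. Two or more units already qualify on their own, so at that threshold the answer matters only for subjects given a single unit.

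**Cost.** One more assay on each of two existing draws and a few case report form fields, with no added visit or needle stick. More bleeds may be classed as major, so the reported rate could be slightly less favourable.
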